### **13.2. Medications (medications related to Serious Adverse Events only)**

The number and percentage of subjects in the Transplanted Recipient Population taking any medications for SAEs reported within the first 30 days or until initial hospital discharge (which ever occurs later) will be presented. The number and percentage of subjects taking any medications for these reported SAEs will also be tabulated by therapeutic category and generic name. Descriptive statistics will be presented for the duration of use for each type of medication administered. If the same medication is used multiple times, the duration of use is the sum of the durations of all periods. Patients who do not use a given type of medication will be excluded from the analysis for that type of medication. If a patient is continuing to use a given type of medication at the time of completion/discontinuation, the time of completion/discontinuation will be considered the stop time for that patient for that type of medication in calculating the duration of use.

The number and percentage of subjects in the Transplanted Recipient Population will be presented using each type of immunosuppressive therapy (ATG, OKT3, IL2 receptor agonist, cyclosporine, tacrolimus, azathioprine, mycophenolate, steroids, sirolimus, eurolimus, other, and any immunosuppressive medication) at any of the following timepoints: induction, Day 7, or discharge.

## **14. OTHER ANALYSES**

Kaplan-Meier estimated freedom from BOS and BOS-free survival time probabilities will be presented for the following nominal timepoints: Day 30, 6 months, 12 months, 24 months, and 36 months.

Chest radiograph data at transplant and post-transplant timepoints will be summarized using descriptive statistics.

Recipient bronchoscopy data at discharge, 6 months, 12 months, 24 months, and 36 months will be summarized using frequencies and percentages. Transbronchial biopsy results at discharge, 6 months, 12 months, 24 months, and 36 months will be summarized using frequencies and percentages. Recipient pulmonary function test results at discharge (or up to the first 90 days post transplant if not done at discharge), 6 months, 12 months, 24 months, and 36 months will be summarized using descriptive statistics. Recipient data at the 6, 12, 24 and 36 month follow-up visits (was patient withdrawn from the study since the last visit and, if so, the reason for withdrawal, did recipient survive, did the lung graft survive, was there a diagnosis of post-lung transplant Bronchiolitis Obliterans Syndrome since the last visit, was recipient hospitalized since the last follow-up visit) will be summarized using frequencies and percentages.

The number and percentage of patients having mechanical circulatory or ventilator support (i.e., ECMO, any ventilator support, any support) within 30 days post-transplant or until initial discharge (whichever occurs later) will be presented. For each type of support, the table will present descriptive statistics for the time from surgery to the start of the first occurrence of support and for the duration of support. Patients who do not

use a given type of support will be excluded from the analyses for that type of support. If a patient is continuing to use a given type of support at the time of completion / discontinuation, the time of completion / discontinuation will be considered the stop time for that patient for that type of support in calculating the duration of support. If the same support is used multiple times, the duration of support will be the sum of the durations for all periods.

The analyses described above will be performed for the PP and Transplanted Recipient Populations.

OCS parameters at the initial assessment at the beginning of OCS preservation and at the final assessment at the end of OCS preservation will be summarized for the PP and Transplanted Recipient Populations using descriptive statistics.

Donor lung OCS instrumentation data for the PP and Transplanted Recipient Populations will be presented using descriptive statistics for continuous variables and frequencies and percentages for categorical variables.

OCS perfusion times (lung preservation duration on the OCS Lung System) for the PP and Transplanted Recipient Populations will be presented using descriptive statistics.

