## 3. STUDY DESIGN

### 3.1. Overview

This is a prospective, pivotal, international, single-arm trial of donor lungs and donor lung transplant recipients.

The proposed clinical trial seeks to evaluate the safety and effectiveness of the OCS™ Lung System for donor lungs that today may not be transplanted due to the limitations associated with cold storage technique (such as ischemia and the inability to evaluate organ function following cold preservation). The results of the OCS™ Lung System with non-ideal donor lungs in this study will be compared to the results for both the control arm of the INSPIRE trial and to the results of the NOVEL study of the XEVIVO EVLP system.

Subjects will be followed for up to 36 months from the date of transplantation. The details of the follow-up are summarized in Appendix 4 of the Protocol as follows:

- All subjects will be followed from transplant to discharge.
- Patient survival will be documented on Day 30 post-transplant and at initial hospital discharge following transplantation (if longer than 30 days).
- Patient survival and clinical diagnosis of BOS will be documented at 6, 12, 24, and 36 months patient follow-up (these are post-market follow-up timepoints) per Appendix 4 of the Protocol.

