### **5. STATISTICAL CONSIDERATIONS**

#### **5.1. General Methodology**

All statistical analyses will be performed and all tables and listings will be produced using SAS® Version 9.4 or higher.

The study was designed for 90 transplanted recipients in the U.S. and world-wide (Europe, Australia and Canada).

Continuous variables will be summarized using descriptive statistics, specifically the mean, median, standard deviation, minimum and maximum. Categorical variables will be summarized using frequencies and percentages. All statistical tests will be performed at the 0.05 significance level, unless otherwise specified in this document.

All data collected will be included in the data listings. Data listings will be sorted either by recipient ID or by donor ID, as appropriate. All date fields will be presented in a format of ddmmmyyyy (e.g., 01Jan2017) in the listings.

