### **12.4. Other Effectiveness Endpoints**

Other effectiveness endpoints are as follows:

- Total ischemia and cross-clamp times
- Duration of initial post-transplant invasive mechanical ventilation
- Length of initial post-transplant ICU stay
- Length of initial post-transplant hospital stay
- PGD Scores at T0, T24, T48, and T72 hours
- Incidence of BOS at 6, 12, 24, and 36 months post-transplantation (including post-market follow-up)
- All-cause mortality at 6, 12, 24, and 36 months post-transplantation (including post-market follow-up)
- Lung graft-related mortality at 6, 12, 24, and 36 months post-transplantation (including post-market follow-up).

These endpoints will be summarized for the PP and Transplanted Recipient Populations using descriptive statistics and 95% confidence intervals for the true mean based on the t-distribution for continuous endpoints and using counts and percentages and exact (Clopper-Pearson) 95% confidence intervals for categorical endpoints.

Survival will also be displayed using the Kaplan-Meier product-limit method.

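### SAP 14 plans Kaplan-Meier freedom from BOS with no rule for deaths; if they are censored, one minus the curve overstates the probability of developing BOS

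*SAP*

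**What the plan says.** SAP section 14 (Other Analyses) states: "Kaplan-Meier estimated freedom from BOS and BOS-free survival time probabilities will be presented for the following nominal timepoints", namely "Day 30, 6 months, 12 months, 24 months, and 36 months". It gives no event definition, no censoring rule and no statement on recipients who die before BOS. Neither the SAP nor the protocol mentions competing risks or cumulative incidence.

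SAP section 12.4 lists "Incidence of BOS at 6, 12, 24, and 36 months post-transplantation" among the other effectiveness endpoints and summarises it "using counts and percentages and exact (Clopper-Pearson) 95% confidence intervals for categorical endpoints". The same list has "All-cause mortality at 6, 12, 24, and 36 months post-transplantation", and a Kaplan-Meier display of survival is added. No denominator is given for the BOS percentage once recipients have died.

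SAP section 3.1 sets the horizon: "Subjects will be followed for up to 36 months from the date of transplantation". SAP section 5.3 sends missing outcomes to multiple imputation so that the data are complete, and does not exempt BOS status after death.

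**The concern.** A recipient who dies without BOS can never develop it. A Kaplan-Meier curve that censors that recipient passes their weight to those still at risk, as though the recipient would have gone on to face the survivors' BOS risk. One minus the curve is then at or above the proportion who actually develop BOS, with equality only if nobody dies first.

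At stake is how the long-term BOS results are read. The protocol's account of INSPIRE (section 1.4.3) treats a lower BOS rate through 24 months as an important clinical benefit, so readers are likely to look at the EXPAND II BOS figures and set them beside other series. With deaths present, the Kaplan-Meier figure in SAP 14 and the percentage in SAP 12.4 can differ, and the plan does not say which one is the incidence or how deaths enter either.

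**Working it through.** **What the plan gives.** There is no figure to reproduce: the documents contain no BOS rate and no 36-month mortality. They give early survival only: 93.9% (169/180) in the INSPIRE control arm (SAP 12.1), so 11/180 = 6.1% early deaths, and 98% at 30 days and 95% through the initial hospitalization in EXPAND I (protocol 1.4.4). The planned size is 90 (SAP 5.1: "The study was designed for 90 transplanted recipients").

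**Assumptions.** Constant, independent hazards over 36 months. Let K be one minus Kaplan-Meier for BOS at 36 months with deaths censored. Let d be the probability of death without BOS by 36 months when BOS is ignored. K is varied from 10% to 50%. d is varied from 6.1% (the INSPIRE early-death rate, used as a floor) to 40%. All of these except the 6.1% are assumed.

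**Formulas** (cumulative hazards to 36 months):

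- B = −ln(1 − K)
- D = −ln(1 − d)
- cumulative incidence of BOS = B/(B + D) × [1 − exp(−(B + D))]
- excess = K − cumulative incidence

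**Example, K = 30%, d = 30%.** B = D = 0.3567. Cumulative incidence = 0.5 × (1 − 0.70 × 0.70) = 0.5 × 0.51 = 25.5%. Excess = 4.5 points.

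**Results for K = 30%:**

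| Death without BOS, d | Cumulative incidence | Excess (points) |
|---|---|---|
| 6.1% | 29.1% | 0.9 |
| 10% | 28.6% | 1.4 |
| 20% | 27.1% | 2.9 |
| 30% | 25.5% | 4.5 |
| 40% | 23.8% | 6.2 |

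**Ends of the grid.** K = 10%, d = 6.1%: 9.7% against 10%, excess 0.3 points (ratio 1.03). K = 50%, d = 40%: 40.3% against 50%, excess 9.7 points (ratio 1.24). The largest ratio is 1.27, at d = 40% with K of 10% or 20%.

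**Early deaths.** If all 6.1% die before any BOS risk and nobody dies later, cumulative incidence = 0.939 × K. For K = 20%, 30% and 40% that is 18.8%, 28.2% and 37.6%, an excess of 1.2, 1.8 and 2.4 points.

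**Against sampling error.** Simulating 90 recipients gave a mean one-minus-Kaplan-Meier of 30.0% against 27.0% by Aalen-Johansen at d = 20%, and 30.1% against 25.5% at d = 30%. The Kaplan-Meier standard error was 5.1 and 5.5 points. The bias is thus within about one standard error at these rates, but it is systematic and a confidence interval around the curve does not allow for it.

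**The case against.** The strongest reply is that four things a reader might infer are not in the documents.

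- **That the SAP prescribes censoring at death.** It is silent. Censoring is inferred from freedom from BOS being listed apart from BOS-free survival. No other reading is as natural, but what can be verified is the missing definition.
- **That the listed BOS incidence endpoint is biased.** SAP 12.4 analyses it by counts and percentages, not by one minus Kaplan-Meier, and SAP 14 never calls its curve the incidence. With complete follow-up and all transplanted recipients in the denominator, the crude percentage equals the Aalen-Johansen estimate. The denominator is, however, not stated, and there is no rule for deaths or loss to follow-up.
- **That 36-month mortality is known to be substantial.** No such figure appears. Nor can overall mortality simply be used as d: some deaths follow BOS, which protocol 1.4.3 itself links to re-transplant or death. For instance, with assumed 3-year survival of 65% and K = 50%, treating mortality as equal with and without BOS gives an excess of 8.4 points. Assuming post-BOS mortality three to five times the pre-BOS rate brings it to roughly 5 to 6.
- **That the method flatters the device or threatens the trial's conclusions.** Overstating BOS works against the device, no hypothesis is tested on it, no BOS comparison with another trial is specified, and the benefit language in protocol 1.4.3 describes INSPIRE. BOS-free survival and all-cause mortality are also reported.

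All four limits stand. They shrink the point but do not remove it: the curve is planned, its handling of death is undefined, and its most likely form cannot be read as the probability of developing BOS.

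**Conclusion.** The point holds as a gap in a descriptive analysis. SAP 14 plans a freedom-from-BOS curve without event or censoring rules. If deaths without BOS are censored, the direction of the error is certain: one minus the curve is too high whenever someone dies before BOS. The size is not known. It is about 0.3 to 9.7 points over the assumed grid and about 1 to 6 points at a one-minus-Kaplan-Meier of 30%, given constant, independent hazards. No primary, secondary or safety conclusion changes. The case for acting is that the remedy is nearly free and uses survival and BOS data already collected at these visits.

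**What to change.** In SAP 14, at the same timepoints, report the Aalen-Johansen cumulative incidence of BOS with death and re-transplant as competing events, either in place of Kaplan-Meier freedom from BOS or as the main presentation ahead of it. Keep BOS-free survival. For each curve, state what counts as the event and when follow-up is censored. In SAP 12.4, state that the BOS percentages keep recipients who have died in the denominator. In SAP 5.3, state that BOS is not imputed after death.

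The cost is a few SAP sentences and one extra standard output, with no new data collection and no effect on sample size or on any test.
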